< 0.01) compared to placebo controls.¹⁸ These regimens were *ultra*-short in duration (≤ 5 days) and in some studies included a postoperative dose.^{15,17,26} No differences in adverse events were noted in the 810 subjects enrolled in these studies. However, none of these studies were sufficiently powered to detect either differences in clinical outcome or safety. As such, the beneficial effects of an *ultra*-short course of EPO remain uncertain. Studies from the orthopedic surgery literature suggest that longer treatment intervals will likely be required to increase red blood cell mass to a level capable of reducing erythrocyte transfusions to the degree needed to detect an independent effect on clinical outcome. Prolonged use of these agents (EPO, darbepoetin) in patients with cardiovascular disease and heart failure have been shown to be safe.^{27,28} The Study of Anemia in Heart Failure Trial (STAMINA-HeFT), the largest of these multicenter, randomized, controlled trials, demonstrated that darbepoetin was effective in raising the hemoglobin levels (1.8g/dL vs. 0.3g/dL; $p < 0.001$) without increasing the risk of ischemic complications.²⁸ In fact, a trend towards lowering the risk of morbidity and mortality was observed in the 162 subjects enrolled in the treatment group.

Overuse of EPO in patients undergoing cardiac surgery needs to be monitored. A study by D'Ambra et al.¹⁵ demonstrated that aggressive dosing of this agent in *non*-anemic patients could be problematic. Given its potential to contribute to a pro-thrombotic phenotype in some individuals, even its short-term use in patients with unstable angina is discouraged by the cardiac surgery practice guidelines.¹⁴ Its black box warning for chronic use in patients with end stage renal disease with cardiovascular disease is also intended to minimize the risk of a thrombotic event. The package insert for darbepoetin also recommends holding scheduled doses should the rise in hemoglobin level exceed 1g/dL per week based on an analysis of their safety data.²⁹⁻³⁰ The creation of a surveillance strategy is one method to increase the safety of EPO use by monitoring patient characteristics that may present an increased risk of a thrombotic event in this clinical setting. This strategy could include:

- 1) limit use to those with preoperative anemia;
- 2) hold scheduled doses in those with hemoglobin thresholds deemed to be safe;
- 3) limit the duration of treatment or total number of doses;

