Anemic patients scheduled to undergo CABG, valve, or CABG/valve surgeries will be considered for the study. Patients who fulfill all the inclusion/exclusion criteria will be asked to participate in the study. The proportion of screen failures and eligible patients who refuse to participate will be recorded using a screen failure log. Patients who agree to be in the study and sign an informed consent form will be sequentially enrolled into the treatment group. The treatment group will receive up to three doses of EPO 300U/kg. The first dose of study medication will be administered up to 28 days before the day of surgery and the second will be administered 1-7 days before the day of surgery. These first two doses will be given at least 7 days apart. A third dose may be administered two to four days following surgery. All 3 doses will be administered subcutaneously and per surveillance strategy guidelines. In addition, supplementation

with IV iron (feraheme; 510mg delivered per IV infusion over a minimum of 15 minutes) will be given following the first two preoperative doses of EPO.

Differences in hemoglobin levels and reticulocyte counts from baseline to the day of surgery (preop to POD#0) and postoperative day five (POD#5), proportion of patients receiving erythrocyte transfusions and number of blood products (RBC, platelets and plasma) utilized and pre-defined clinical events (mortality, major cardiac, renal, neurological events [associated with anemia] and infection) will be assessed in all treated participants. Each patient will be enrolled in the study up to 28 days before the day of surgery and for up to 30 days following the day of surgery. This feasibility propensity-matched study will sequentially enroll 23 more treatment subjects to total 25. The propensity-matching control group will be comprised of 25 total “like” patients for comparison. The source of the data for the control group will be the Society of Thoracic Surgery (STS) Database, an institutional registry.

Study medications:

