The decision to initiate and continue administering doses of EPO is based on evidence accrued from randomized controlled trials and clinical practice guidelines provided by multiple sub-specialty and international societies.^{14,40-41} Substantial heterogeneity exists in factors that could be included in a surveillance strategy to minimize the risk of a thrombotic event in this setting; with no one strategy proven to be superior. The surveillance strategy included in this protocol derives from, what we believe to be, the most current safety analyses of perioperative EPO use reflected in the literature. Implementing such surveillance methods are intended to minimize the possibly rare but potentially life-threatening adverse events. Risk factors considered in our surveillance strategy include: evidence of unstable angina or myocardial infarction, recent thrombotic event, hemoglobin levels associated with a higher risk of a

myocardial event, excessive thrombocytosis (platelet count $>300 \times 10^3/\mu\text{L}$) or laboratory evidence of a hypercoagulable postoperative state.

EPO dosing will be stratified based on patient risk (degree of perioperative anemia), type of procedure (CABG vs. valve) and laboratory data (Hb, RoTEM: MCF) in the following manner:

Initial dosing/Re-dosing of EPO plus IV iron (Prior to Surgical Procedure):

Therapy or a dose will **NOT** be administered in patients under the following conditions:

- Patients scheduled for a CABG procedure with Hb concentration $\geq 12.5\text{g/dL}$
- Patients scheduled for a cardiac valve procedure with Hb concentrations $\geq 13.5\text{g/dL}$
- Rate of rise in Hb level that exceeds 1g/dL in past 7 days (and not secondary to erythrocyte transfusion)^a
- Evidence of any new or evolving symptoms or signs suggesting the presence of myocardial ischemia, including chest pain, EKG changes, or elevation of laboratory cardiac biochemical (CK-MB, Troponin)
- Average of three diastolic blood pressures (over 1hr) $>100\text{mmHg}$ despite scheduled anti-hypertensive therapy.

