^a **Rationale:** The original label for EPO²⁹⁻³⁰ included a warning regarding the risk of exacerbation of hypertension with hematocrit increases exceeding 4 percentage points (corresponding to increases in the hemoglobin concentration of approximately 1.3 g per deciliter) within a 2-week period. During a review of the marketing application, an association was found between rates of increase in the hemoglobin level exceeding 1g/dL per 2-week period and the risk of cardiovascular and thromboembolic events. This observation provided the basis for a warning on the package insert for darbepoetin regarding excessive rates of increase in hemoglobin concentrations.

Continuation of Dosing of EPO (Post-Operative Administration)

Postoperative therapy will **NOT** be administered in patients under the following conditions:

- Hb concentration $>10.0\text{g/dL}$ (both CABG and valve procedures)^b
- Rotational Thromboelastogram (RoTEM) measurement of Maximum Clot Firmness (MCF) $>70\text{mm}$ (RoTEM to be performed during procedure and 2-4 days after surgery, prior to re-dosing).
- Evidence of any new or evolving symptoms or signs suggesting the presence of myocardial ischemia, including chest pain, EKG changes, or elevation of laboratory cardiac biomarkers (CK-MB, Troponin) that have failed to have a decreasing trend
- Average of three diastolic blood pressures (over 1hr) $>100\text{mmHg}$ despite scheduled anti-hypertensive therapy.

^b **Rationale:** A multi-center study in over 2,000 CABG patients by Spiess et al.¹² demonstrated that hematocrit $>34\%$ (11.3g/dL) upon entry in the ICU was the single greatest predictor of myocardial infarction following surgery. Furthermore, according to the labeling for EPO targeting higher hemoglobin (13 to 14g/dL) compared to a lower range (9 to 11.3g/dL) increased the risk of death, myocardial infarction, stroke, and thrombotic events in patients *with CKD*.²⁹⁻³⁰

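### The EPO hold lists contain no explicit stop for a new non-coronary thrombotic event arising after the baseline eligibility check

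*Combined protocol and SAP*

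**What the plan says.** The Background (Section II) describes the purpose of surveillance as "monitoring patient characteristics that may present an increased risk of a thrombotic event in this clinical setting". Section III, Surveillance Strategy for ESA Dosing, then names five risk factors. The sentence begins "Risk factors considered in our surveillance strategy include: evidence of unstable angina or myocardial infarction, recent thrombotic event" and goes on to hemoglobin level, "excessive thrombocytosis (platelet count" above 300 x10^3/µL), and laboratory evidence of a hypercoagulable state after surgery. The next paragraph says that dosing is stratified by degree of anemia, type of procedure and "laboratory data (Hb, RoTEM: MCF) in the following manner". Two lists of conditions for withholding a dose follow, one before and one after surgery.

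On timing, the design summary says of the preoperative doses: "These first two doses will be given at least 7 days apart". Of the postoperative dose it says: "A third dose may be administered two to four days following surgery". The visit description under Post-Operative Dose is firmer: treated patients will be given that injection if they satisfy the surveillance criteria.

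Section VII excludes patients with thromboembolism in the past year or stroke in the past 6 months. Table 1 marks the inclusion and exclusion check in the 7-28 day preoperative column and in no other.

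**The concern.** Thrombosis is the hazard that the surveillance strategy exists to control, and Section X describes this use of EPO as off-label. Yet the postoperative list stops a dose for a laboratory marker of clotting tendency, and neither list stops one for a diagnosed DVT or stroke. Section XI.C counts thrombotic complications among the safety endpoints but attaches no dosing consequence to them.

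There is a second, smaller consequence. Under Clinical Outcomes, the primary objective measures adherence on the doses that the surveillance strategy deems appropriate. If a dose is withheld for a reason found in the narrative but not on a list, the protocol does not say clearly whether that dose counts.

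**Working it through.** No power or sample-size figure bears on this point. The check sets each named risk factor beside the two hold lists and the other safety text, then derives the length of the window from the dosing schedule.

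| Risk factor named in the narrative | Preoperative list | Postoperative list | Elsewhere |
|---|---|---|---|
| Unstable angina or MI | New or evolving myocardial ischemia | Same, including biomarkers that are not falling | Unstable angina excluded at entry (Section VII) |
| Recent thrombotic event | None | None | Past events excluded at entry (Section VII) |
| Hemoglobin level | ≥12.5 g/dL (CABG), ≥13.5 g/dL (valve), or a rise >1 g/dL in 7 days | >10.0 g/dL | Entry requires <13.0 g/dL (Section VI) |
| Platelets >300 x10^3/µL | None | None | Lower limit only, 50,000/mm³ (Section VII) |
| Hypercoagulable state after surgery | Not applicable | MCF >70 mm | None |

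Both lists also hold a dose when the mean of three diastolic readings exceeds 100 mmHg.

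**What the existing items catch.** The ischemia items cover coronary events, and probably a pulmonary embolism that presents with chest pain, EKG change or raised biomarkers. They do not cover a DVT or a stroke. The item "Rotational Thromboelastogram (RoTEM) measurement of Maximum Clot Firmness (MCF") above 70 mm applies only after surgery and measures clotting tendency, not a diagnosed event. Section X adds one hold outside the lists, for blood pressure above 180/100 mmHg. That includes a systolic limit which the lists lack.

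**Length of the window.** Take surgery as day 0. Dose 1 falls on days −28 to −7 (baseline visit), dose 2 on days −7 to −1 and at least 7 days after dose 1, and the postoperative dose on days +2 to +4.

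- Dose 1 to dose 2: shortest 7 days (the required gap); longest −1 − (−28) = 27 days.
- Dose 1 to postoperative dose: shortest 2 − (−7) = 9 days; longest 4 − (−28) = 32 days, with the operation in between.

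**Number of doses concerned.** The study "will sequentially enroll 23 more treatment subjects to total 25". Each patient can have at most two EPO doses after the first, so the gap bears on at most 25 × 2 = 50 doses. How many would follow a new thrombotic event cannot be worked out from the documents.

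**The case against.** The strongest reply is that the gap is one of wording and that practice would close it.

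- **The exclusions may continue to apply.** Section VII sets no end date. One exclusion refers to blood pressure control at the time of the procedure, and one inclusion criterion to a pregnancy test in the week before it, so eligibility is not purely a baseline matter. A clot after dose 1 would also lie within the past year. This reading is possible, but Table 1 schedules no second check, so the text is ambiguous.
- **Clinicians would withhold EPO anyway.** Probably so. The design summary is permissive about both the number of doses and the postoperative dose, and the research nurse visits daily for the first 7 postoperative days. A recognised preoperative event would plausibly also postpone elective surgery, and dose 2 with it. All this limits the exposure. But the visit text makes the postoperative dose follow from meeting the surveillance criteria, and those criteria do not mention the event.
- **The choice of factors is a matter of design.** The protocol says that no single strategy has been shown to be best, and naming a factor as considered does not promise a hold for it. This stands for platelets. The sentence on laboratory drivers names only hemoglobin and MCF, so the platelet phrase may be a leftover. A reader might infer a missed safety threshold, but the documents show no consequence from it.
- **Adherence.** A reader might infer that a dose withheld for a new DVT would be scored as a failure. The documents do not establish that. The sentence naming the risk factors sits inside the surveillance section, so such a dose can equally be read as not appropriate and outside the count.
- **Event rates.** Section X lists DVT among reactions seen in over 5% of EPO-treated perioperative patients. A reader might take this as the expected rate here. It has no comparator, the same section warns that trial rates may not carry over, and it reports no observed increase in thrombotic events at the institution over more than 2 years of use.

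**Conclusion.** The point holds with moderate confidence as a cheap improvement. The narrative names recent thrombotic event as a surveillance factor, and neither list stops a dose for a new DVT, stroke, or pulmonary embolism without ischemia-like signs after the baseline check. Withholding EPO then rests on judgement, or on reading the exclusions as continuing, across a window of up to 27 days before dose 2 and up to 32 days before the postoperative dose.

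The conclusion assumes that the lists are the operative dosing criteria and that eligibility is checked only where Table 1 marks it. It does not show that any patient would be dosed after a clot, and the rate of such events is unknown. A reader might infer that the protocol intends dosing to continue after a thrombosis. The permissive dosing language and the stated purpose of surveillance point the other way. The platelet threshold is a secondary mismatch of wording.

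**What to change.** 1. Add to both hold lists, as an EPO hold: any new thrombotic or thromboembolic event since enrolment, using the STS definitions that Clinical Outcomes already adopts. The preoperative list also governs IV iron, so state that this item stops EPO and that the clinical lead decides on iron.
2. Align the lists' diastolic-only limit with the 180/100 mmHg hold in Section X.
3. State in the adherence definition that a dose withheld under a listed hold does not count as non-adherent, and record the reason for each withheld dose.
4. Either adopt platelets >300 x10^3/µL as a hold, using the CBC already in every column of Table 1, or delete the phrase from the narrative. The documents do not say how often that count would be exceeded, so the number of doses lost by adopting it is unknown.

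The cost is amendment wording and one or two lines on the dosing checklist, with no new test or visit. The downside of the thrombosis hold is that an occasional dose is withheld, with a smaller hemoglobin response in that patient.

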Screening for Potential Participants: A HIPAA waiver was obtained to allow the research team to screen the medical records of patients scheduled for CABG, valve or CABG/valve surgery at UTSW University Hospital eligible for participation in this study. At the initial consultation with the cardiothoracic service or through Patient Blood Management Clinic, patients who fulfill the initial entry criteria for the study will be invited to participate in this propensity-matched study for patients with “low preoperative blood counts (or anemia)”. Patients who agree to be part of the study will be approached by members of the research team, who will explain the protocol in detail and will ask the patient to sign a written informed consent. Patients that become aware of the trial via the UT Southwestern clinical research website, will be referred directly to the clinical research nurse to answer all their questions and be encouraged to discuss possible participation with their surgeon during their next appointment.

Baseline Research Visit (7-28 days before day of surgery):

- Patients will be asked to sign the informed consent and HIPAA forms should they decide to proceed with the study.
- Patients will be escorted from the cardiothoracic surgery clinic by a member of the clinical research team or asked to come to the UTSW Patient Blood Management Clinic, Zale Lipshy University Hospital at [name]
- Data on demographics, vital signs, medical history, current medications, height, and weight will be recorded.
- We will review all available lab results.
- The patient will be enrolled into the treatment group.
- Treatment group patients will receive a single subcutaneous injection of EPO 300U/kg and an IV iron infusion of 510mg. Vital signs including heart rate, blood pressure, oxygen saturation, and temperature will be recorded before, during, and after drug administration.
- Patient will be monitored for any serious reactions during drug administration and for at least 30 minutes following each infusion. Serious reactions include anaphylaxis, chest pain, dyspnea, seizures, severe headache, fever, nausea, vomiting, and diarrhea, an increase in blood pressure greater than 20mmHg above baseline systolic, systolic BP greater than 180mmHg and/or diastolic BP greater than 100mmHg, hypotension.
- The visit will last approximately 1.5 hours.

Pre-op Visit (1-7 days before surgery)

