1. The subject must be between the age of 18 and 80 years old.
2. The subject must be diagnosed with preoperative anemia, defined as hemoglobin <13.0g/dL.
3. The subject must be scheduled for elective cardiac surgery (CABG, valve, or CABG/valve), including both first time and repeat procedures.
4. Female subjects of child bearing potential must have a documented negative pregnancy test within 7 days prior to the procedure.

5. The subject must sign a written informed consent prior to the procedure, using a form that is approved by the UT Southwestern Institutional Review Board.
6. The subject must agree to be compliant and return for all follow-up visits.

VII. CRITERIA FOR EXCLUSION OF SUBJECTS:

The subjects will be excluded if they meet any one of the following criteria:

1. Uncontrolled hypertension (defined as systolic pressure greater than 180mmHg, diastolic pressure greater than 100mmHg, not adequately controlled by anti-hypertensive therapy at the time of procedure).
2. Current renal failure on dialysis or serum creatinine [Cr]>3.0mg/dL. ¹
3. Unstable angina (defined by chest pain and ECG changes indicating ischemia at rest).
4. Thromboembolism within the past year.
5. Current active primary or metastatic malignancy or history of myeloid malignancy.
6. Seizures within the past year.
7. History of stroke within the last 6 months.
8. Patients who have platelet count lower than 50,000/mm³ or coagulation abnormality.
9. Sepsis or bacteremia defined by positive blood culture.
10. Patients who have known hypersensitivity to EPO or any of its components.
11. Patients who have known hypersensitivity to Feraheme or any of its components.
12. Patients who refuse blood transfusion, (i.e. Jehovah's Witnesses).
13. Pregnant or breast feeding.
14. Patients who are unable to provide informed consent or who has inability to understand or cooperate with study procedure.

VIII. SOURCES OF RESEARCH MATERIAL

Data will be obtained from the patient's medical records EPIC and the Society of Thoracic Surgery (STS) database entries. Laboratory tests for reticulocyte count and additional serum ferritin, cardiac biomarkers, serum creatinine, thromboelastographic and liver transaminase measurements will be obtained specifically for research purposes. Other tests conducted (e.g. hemoglobin concentration, creatinine, EKG) will be part of standard of care (see Table 1 for details regarding standard of care and for research only).

IX. RECRUITMENT METHODS AND CONSENTING PROCESS

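### The systolic 180 mmHg dose hold stated in the risk section is missing from both EPO hold lists; a lesser gap lets CABG patients at Hb 12.5-12.9 g/dL enrol without the first dose

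*Combined protocol and SAP*

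**What the plan says.** **Blood pressure.** Section X (Potential Risks) reports hypertension as the only side effect seen locally with these agents and says treatment will be held above 180/100 mmHg. The dosing decision itself is made from two lists in Section III under Surveillance Strategy for ESA Dosing: one for initial dosing and re-dosing before surgery, one for the postoperative dose. The blood-pressure item is the same in both. It starts "Average of three diastolic blood pressures (over 1hr", sets the limit at more than 100 mmHg despite scheduled treatment, and gives no systolic figure. Section III (Research Design and Methods) ties every dose to these lists: "All 3 doses will be administered subcutaneously and per surveillance strategy guidelines". The Pre-op Visit and Post-Operative Dose instructions refer to them again.

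**Hemoglobin.** Section VI item 2 sets one ceiling for all procedures: "The subject must be diagnosed with preoperative anemia, defined as hemoglobin <13.0g/dL". The preoperative list withholds therapy from "Patients scheduled for a CABG procedure with Hb concentration" of 12.5 g/dL or more, and from "Patients scheduled for a cardiac valve procedure with Hb concentrations" of 13.5 g/dL or more. The Baseline Research Visit text, after the enrolment step, says: "Treatment group patients will receive a single subcutaneous injection of EPO 300U/kg and an IV iron infusion of 510mg". That bullet does not mention the surveillance rules. On size, Section III says: "This feasibility propensity-matched study will sequentially enroll 23 more treatment subjects to total 25".

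**The concern.** The hold lists are the working safeguard for an off-label drug whose most common serious adverse effects, according to the protocol, include hypertension. A limit that appears only in the risk narrative is easily missed by whoever decides doses 2 and 3, because the visit instructions send that person to the lists.

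The hemoglobin point matters less. A CABG patient can meet the entry criterion, be enrolled in the treatment group and then be refused the baseline dose. That patient would hold a place in a 25-patient pilot without receiving the planned course. The adherence measure would not show it, because adherence is counted only over doses that the surveillance strategy deems appropriate.

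**Working it through.** The documents give no figure to reproduce here. The check sets the limits side by side.

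**Where each blood-pressure limit stands**

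| Place | Systolic >180 | Diastolic >100 | Function |
|---|---|---|---|
| Section X, Potential Risks | yes | yes | statement that treatment is held |
| Section III, preoperative list | no | yes (average of three over 1 hr) | decides doses 1 and 2 |
| Section III, postoperative list | no | yes (average of three over 1 hr) | decides dose 3 |
| Section VII item 1 | yes | yes | eligibility |
| Section III, visit instructions | yes | yes | reaction to monitor |

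Test case, 190/95 mmHg: 190 > 180, so Section X would hold the dose. Since 95 ≤ 100, the blood-pressure item in neither list is triggered. The uncovered set is systolic above 180 with average diastolic at or below 100.

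By dose:
- Dose 1 is partly covered. Table 1 (Section IV) schedules the eligibility check at the 7-28 day visit, where the Section VII systolic exclusion applies. Section IX lets the dose be given at a separate appointment, so the cover is not complete.
- Doses 2 and 3 have no eligibility check in Table 1. For 2 of the 3 doses, the list used to decide them is the only scheduled gate, and it has no systolic limit.

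**Hemoglobin: eligible range against hold range**

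- CABG: Hb < 13.0 and Hb ≥ 12.5 overlap at 12.5 ≤ Hb < 13.0, that is 12.5-12.9 g/dL to one decimal. These patients are eligible but barred from the initial dose.
- Valve: Hb < 13.0 and Hb ≥ 13.5 do not overlap. No eligible valve patient is barred at baseline on Hb level.
- CABG/valve: the patient is scheduled for CABG, so on an ordinary reading the CABG item applies and the limit is 12.5. The list does not say so.

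Each patient in the overlap is 1/25 = 4% of the treatment places. With 23 still to enrol, 25 − 23 = 2 appear to be enrolled already. The documents give no Hb distribution by procedure and no rate of systolic >180 with diastolic ≤100, so neither frequency can be computed.

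**The case against.** **On blood pressure.** Section X is protocol text, and staff can obey it and the lists together, so this is an omission from the lists and not an incompatibility. A reader might infer that the protocol permits dosing above 180 systolic; it does not. The visit instructions also put systolic 180 in front of staff when doses 2 and 3 are given, with pressure recorded beforehand. All of this stands, but none of it makes systolic 180 a hold in the place where the decision is made. One could also read 180/100 as requiring both limits to be exceeded, in which case the diastolic item alone would be enough. The visit instructions join the same two limits with and/or, which favours reading either one as sufficient.

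**On hemoglobin.** The objection is stronger here. Section III promises up to three doses, all under the surveillance rules. The preoperative list is headed for initial dosing as well as re-dosing, so withholding the first dose is foreseen and is not a protocol deviation. An entry ceiling above a dosing limit can be deliberate. Laboratory results are reviewed before the enrolment step, and Section IX has patients judged appropriate before they are invited. What remains is a baseline bullet without a cross-reference and no rule on whether an enrollee who misses the first dose counts toward the 25.

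A reader might go further and infer that the pilot's Hb-response estimates are compromised, or that CABG eligibility must drop to 12.5. The documents support neither. Outcomes are to be assessed in all treated participants, so a never-dosed patient need not enter the Hb summary, and the analysis is mainly descriptive. Enrolment rate is part of the primary objective and the proportion eligible is Specific Aim 1. Changing the entry criterion with 2 patients apparently enrolled would split both across two definitions.

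**Conclusion.** The blood-pressure point holds and should be fixed. The systolic limit in Section X is in neither operative list, and doses 2 and 3 have no other scheduled gate that would apply it. This rests on reading 180/100 as either limit being sufficient, and on staff working from the lists as the visit text directs. How many doses are affected is not known.

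The hemoglobin point is secondary. The overlap at 12.5-12.9 g/dL in CABG patients is certain from the thresholds. Its consequence is limited to treatment places that may be filled without the planned first dose, 4% of the group for each such patient. Such a patient could still be dosed later, before surgery if Hb falls below 12.5 or after surgery at Hb 10.0 or lower, if no other hold applies. This calls for a clarification of dosing and counting, not a change of eligibility.

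**What to change.** 1. In the blood-pressure item of both the preoperative and the postoperative list, add systolic >180 mmHg as a hold alongside diastolic >100 mmHg, with either one sufficient. Measure it in the same way: average of three readings over 1 hour, despite scheduled treatment. Section X does not specify averaging for systolic pressure; it is carried over from the diastolic item for consistency.
2. In the Baseline Research Visit, make the EPO and iron bullet subject to the Surveillance Strategy.
3. Count toward the 25 only patients who receive the first dose. Log enrolled patients who do not receive it, so that they stay in the Aim 1 count, and report any later dose they are given.
4. State in the preoperative list that the CABG limit of 12.5 g/dL applies to combined CABG/valve procedures.
5. Leave the Section VI ceiling of 13.0 g/dL unchanged.

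Cost: a few more held doses. Because the preoperative list governs EPO plus IV iron, a systolic hold there would hold the iron too. Blood pressure is already recorded before each dose, so no new type of measurement is needed. Item 3 may mean enrolling a few more patients to reach 25 with a first dose; the documents do not allow that number to be estimated.
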